Research Repositories: If the purpose of this submission is to establish a Research Repository (bank, registry) indicate whether the material you plan to collect would or would not be available from a commercial supplier, clinical lab, or established IRB approved research repository. Provide scientific justification for establishment of an additional repository collecting duplicate material. Describe the repository design and operating procedures. For relevant information to include, see the UK Research Biospecimen Bank Guidance [\[PDF\]](#) or the UK Research Registry Guidance [\[PDF\]](#)

Patient recruitment will be done for the first 42 months of the study after administrative startup (Figure 2). Biochemical measurements, MDCT, QCT and DXA scans, and clinical assessment will be performed at baseline, 6 months, and at 12 months, 18 months and 24 months. Treatment monitoring visits with blood draws (initially bi-weekly or monthly and thereafter every 3 months) and adverse event monitoring phone calls (monthly at least) will occur during years one through five. Interim analyses and first publications will be done once 50% of patients have completed 1 year visits, approximately at the end of Year 3. Final analyses of the data and preparation of abstracts and manuscripts of the obtained results will be completed during year 5. Control patients who completed 1 year of follow up without treatment will be offered additional 2 years of enrollment with treatment according to protocol. Patients who were initially randomized to treatment groups will be offered continued treatment for an additional 1 year to complete 2 years of therapy. Previously enrolled patients will be recruited from the beginning of patient enrollment. These patients will be provided with an additional consent for the extension of the treatment arm.

Figure 2: Study Timeline

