- A compelling rationale for proposed exclusion of any sex/gender or racial/ethnic group;
- The proposed dates of enrollment (beginning and end);
- The proposed sample composition of subjects.

You may reference grant application/sponsor's relevant protocol pages and attach as an appendix using the below attachment button, however, a summary paragraph must be provided in the text box below.

It is anticipated that 990 CKD-5D patients will be enrolled. The study population will include men and women age 21 years and over from various ethnic backgrounds. The enrollment will be done between January 2015 and January 202119.

TARGETED/PLANNED ENROLLMENT: Number of Subjects

Ethnic Category Sex/Gender

Females Males Total

Hispanic or Latino 15 15 30

Not Hispanic or Latino 480 480 960

Ethnic Category: Total of All Subjects * 495 495 990

Racial Categories

American Indian/Alaska Native

Asian 3 3 6

Native Hawaiian or Other Pacific Islander

Black or African American 225 225 450

White 267 267 534

Racial Categories: Total of All Subjects * 495 495 990

Inclusion Criteria:

- Aged 21 years or older;
- Chronic maintenance dialysis of at least 3 months' duration;
- Mental competence;
- Willingness to participate in the study;
- Normal corrected serum calcium.
- Low bone densityOsteoporosis by DXA scan in any site. (T-score = -1-2.5 for men over age 50 or postmenopausal women, or Z-score = --12.5 for all others).

Exclusion criteria:

- Pregnancy or Breast Feeding;
- Incarceration
- Systemic illnesses or organ diseases that may affect bone (except type 1 or type 2 diabetes mellitus);
- Clinical condition that may limit study participation (e.g., unstable angina, respiratory distress, infections).
- Chronic alcoholism and/or drug addiction;
- Known Paget 's disease of bone;
- Prior external beam or implant radiation therapy involving the skeleton, only if randomized to the Teriparatide treatment
- Participation in a study of an investigational drug during the past 90 days;
- Planning to move out of the area within 1 year of the study;
- Scheduled for renal transplantation
- BMD T-score of the radius less than -3.5 by DXA. (if randomized to teriparatide to avoid the known potential negative effects of teriparatide treatment on BMD of the radius)
- Current treatment with medicines containing digoxin;
- More than 3 CT scans in the prior 12 months (to avoid excessive radiation exposure);
- Planned or anticipated oral surgery within the next 12 24 months;

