- Inability to stand or sit upright for at least 30 minutes;
- Treatment within the past 6 months with drugs that may affect bone metabolism including bisphosphonates and teriparitide (except for treatment with calcitriol, Vit D analogs and/or calcimimetics).
- Abnormalities of the esophagus which delay esophageal emptying such as stricture or achalasia;
- Calcidiol levels below the normal range. The current routine clinical practice in our dialysis clinics is to check calcidiol status twice yearly and supplement with vitamin D according to serum calcidiol levels. It is therefore unlikely that a substantial number of patients will be excluded due to this exclusion criterion.

Attachments

Subject Recruitment Methods & Privacy: Using active voice, describe plans for the identification and recruitment of subjects, including how the population will be identified, and how initial contact will be made with potential subjects by those having legitimate access to the subjects' identity and the subjects' information.

Describe the setting in which an individual will be interacting with an investigator or how and where members of the research team will meet potential participants. If applicable, describe proposed outreach programs for recruiting women, minorities, or disparate populations as participants in clinical research. Describe steps taken to minimize undue influence in recruiting potential participants.

Please note: Based upon both legal and ethical concerns, the UK IRB does not approve finder's fees or "cold call" procedures made by research staff unknown to the potential participant.

For additional details, see topic "Recruitment of Subjects/Advertising" on ORI's [IRB Survival Handbook web page](#) and the PI Guide to Identification and Recruitment of Human Subjects for Research [\[PDF\]](#).

Subject Recruitment Methods and Privacy: The study coordinators will visit the patients at the dialysis clinics during their regular treatment hours. The nephrologists at these clinics have worked with us on previous research activity and are willing to cooperate. Patients will be informed about the goals and the protocol of the study. An IRB approved recruitment flyer will be given to patients who are interested in participating in the study. A list of screened patients will be kept under lock and key in the study coordinators' office and on a password protected computer.

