The study coordinators will approach via phone during normal business hours all patients who completed study participation and those currently enrolled in ROD III to discuss the extended enrollment option. All previous patients will be eligible for approaching for the extension regardless of when initial participation was completed. Patients will be informed about the goals and the protocol of the study. A list of screened patients will be kept under lock and key in the study coordinators office and on a password protected computer.

Advertising: Specify if any advertising will be performed. If yes, please see ["IRB Application Instructions - Advertisements"](#) for instructions on attaching copies of the information to be used in flyers or advertisements. Advertisements must be reviewed and approved by the IRB prior to use. For additional details, see topic "Recruitment of Subjects/Advertising" on ORI's [IRB Survival Handbook](#) web page for the *PI Guide to Identification and Recruitment of Human Subjects for Research* [D7.0000] document [\[PDF\]](#). If you will be recruiting subjects via advertising at non-UK owned or operated sites, you should include a copy of written permission from that site to place the advertisement in their facilities.

Note: Print and media advertisements that will be presented to the public also require review by [UK Public Relations \(PR\)](#) to ensure compliance with UK graphic standards, and equal opportunity language. [i](#)

Print advertisements: The study may recruit subjects through flyers, brochures, posters, cards for clinic rooms, Research Spotlights, bookmarks placed on campus and in the surrounding community and region, including but not limited to the UK Medical Center, UK Clinics, Good Samaritan Hospital, student center, UHS, the 5 UK Center for Clinical and Translational Research wall mounts, Cardinal Hill, monitor screens, and area facilities and businesses.

This study may use physician referral letters to community physicians for patient recruitment.

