Patients consenting for baseline measurements will have BMD measurements of the total hip, lumbar spine and radius by DXA and total body scan. We do not use QCT for initial BMD assessment to avoid unnecessary radiation exposure to patients with normal bone mass who will be excluded from the study. Patients who are not do not have low bone densityosteoporotic by DXA T-scores/Z-

scores at any site will be excluded from further participation. Results from our prior funding period study indicate this will be 30% or 178 patients. Those patients who are identified as having low bone density/osteoporotic will have blood draws performed for determination of turnover status (PTH, PTH ratio and TRAP-5b; see Table 1) and baseline biochemical results (serum calcium and BSAP). They will also have BMD measurements of the total hip and spine by QCT, and CAVC measured by MDCT. Patients will be assigned to one of two treatment arms based on their turnover status: 1) low turnover patients and 2) normal or high turnover patients. For each treatment arm we will use adaptive randomization by group completion rates, age race and gender to assign patients to one of two groups A) treatment, and B) no study treatment (standard of care) controls.

For the extension of treatment modification, we will contact all patients who completed one year in either the treatment or control arms. Patients who previously participated in the treatment arm will be offered an additional 1 year of therapy to complete 2 years of therapy. For patients who previously participated in the control arm, they will be offered 2 years of therapy. Both therapies can be given in two consecutive years, or with a time-gap in-between.

TREATMENT PROTOCOLS:

Low Turnover Groups: Patients with low bone turnover will be randomized to receive daily teriparatide injections with cinacalcet or no study treatment, i.e. standard of care, as controls.

Normal or High Turnover Groups: Patients with normal or high bone turnover will be randomized to receive alendronate or no study treatment, i.e., standard of care, as controls. Teriparatide is not justified in these patients because it might worsen underlying high turnover abnormalities and requires avoidable daily injections.

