Both teriparatide and alendronate have been used in low bone densityosteoporotic patients for more than 11 and 15 years, respectively. In the experience of the PI they are generally well-tolerated. The PI has used these medications in his osteoporosis practice in patients with and without CKD for over 10 years and has experience in long-term monitoring of these treatments. Alendronate is indicated for the treatment of low bone densityosteoporosis in postmenopausal women and for treatment to increase bone mass in men with bone lossosteoporosis. Alendronate is contraindicated in patients with the following conditions: abnormalities of the esophagus which delay esophageal emptying such as stricture or achalasia; inability to stand or sit upright for at least 30 minutes; hypocalcemia, that is, blood calcium levels below normal range for the employed assay; prior hypersensitivity to alendronate. Use of alendronate in CKD-5D patients is not specifically mentioned as a contraindication in the package inserts or on the safety web page. However, it is recommended to not give alendronate to patients with GFR < 35 mL/min. A post-hoc data analysis of 581 women with reduced renal function (GFR < 45 mL/min.) who were participating in the fracture intervention trial showed that alendronate was safe and effective.⁶⁰

The major observed side effects for alendronate are gastrointestinal complaints which include abdominal pain, nausea, dyspepsia, constipation, diarrhea, and flatulence. Regurgitation, esophageal ulcer, vomiting, dysphagia, abdominal distention, and gastritis have occurred at a lower frequency. Rarely, taste perversion has been reported. The combination of alendronate and naproxen has been reported as synergistic for development of gastric ulcers. The frequency of adverse effects increases with higher dosages. Adverse effects usually have been mild when patients adhered to prescribing instructions. In a 12-week multicenter, randomized, double-blind, placebo-controlled study of 450 post-menopausal women, the incidence of gastrointestinal side effects was comparable (13% vs. 11%) in the treatment and placebo groups.⁶¹

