Teriparatide for patients with low bone turnover: Patients with increased baseline risk of osteosarcoma will be excluded from this study (Paget's disease of bone, pediatric populations and young adults with open epiphyses, or prior external beam or implant radiation therapy). Our inclusion/exclusion criteria eliminate all of these patients. There are no direct contraindications given for CKD patients given in the package inserts and the safety web page. However, because bone loss with CKD-5D is not specifically addressed in the indications, we have obtained an IND (Investigational New Drug) from the FDA.

If during the monthly monitoring calls/visits or quarterly visits patients complain of new onset adverse reactions such as arthralgia, pain, nausea, dizziness or leg cramps, the patients will be counseled regarding standard treatment measures. Follow-up contact will be made in one week and if symptoms persist, treatment will be discontinued until the next regularly scheduled quarterly monitoring visit. Follow-up communication will occur within 1 week +/- 3 days and if problems persist despite discontinuation, patients will be referred to his/her primary care provider.

If patients complain of injection site reactions, they will be counseled regarding their injection technique and follow-up contact will be made in one week +/- 3 days. If reactions persist, treatment will be discontinued until next regularly scheduled quarterly monitoring visit. If problems persist despite discontinuation, patients will be referred to his/her primary care provider and their participation in the study will end.

In the rare case where PTH level maintenance requires cinacalcet doses that induce serum calcium levels below 8.5 mg/dL, treatment will cease and patients will be excluded from further participation in the study.

Alendronate for patients with normal or high bone turnover: Our inclusion/exclusion criteria cover all of the above-mentioned contraindications. To be safe, we have obtained an IND from the FDA.

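### The protocol says its eligibility criteria cover every listed alendronate contraindication, but prior hypersensitivity to alendronate (1 of 4) is not among them

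*Combined protocol and SAP*

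**What the plan says.** All references are to the Combined protocol and SAP.

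- **Potential Risks** opens its list with "Alendronate is contraindicated in patients with the following conditions" and gives four items. The last two read in part "blood calcium levels below normal range for the employed assay; prior hypersensitivity to alendronate".
- **Safety Precautions**, in the paragraph on alendronate for patients with normal or high turnover, says "Our inclusion/exclusion criteria cover all of the above-mentioned contraindications".
- **Study Population** holds the inclusion and exclusion criteria. The two lines closest to a hypersensitivity rule are "Clinical condition that may limit study participation (e.g., unstable angina, respiratory distress, infections" and "Treatment within the past 6 months with drugs that may affect bone metabolism including bisphosphonates".
- **Study Design** says of the extension: "Control patients who completed 1 year of follow up without treatment will be offered additional 2 years of enrollment with treatment". **Research Procedures** agrees: "For patients who previously participated in the control arm, they will be offered 2 years of therapy". **Subject Recruitment Methods & Privacy** adds "All previous patients will be eligible for approaching for the extension regardless of when initial participation was completed".

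**The concern.** The Safety Precautions sentence assures the IRB, for a use studied under an investigator-held IND, that screening removes every patient for whom the drug is contraindicated. If one of the listed contraindications has no criterion behind it, the assurance is inaccurate, and a patient with a known past reaction can meet every written criterion and be allocated to alendronate.

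A contraindication has to be caught before the first dose. The plan's monitoring comes after it: the calcium check about one week after starting, BSAP at the monitoring visits, monthly contact, and the rules for gastrointestinal complaints and musculoskeletal pain. None of the alendronate-specific complaint rules deals with an allergic reaction.

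What is at stake is patient safety and the accuracy of a safety statement. The estimate of the treatment effect is not in question.

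**Working it through.** No sample size, power or error-rate figure is involved. The check sets the contraindications beside the eligibility criteria.

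**Step 1. Which list is meant.** Potential Risks contains the only list of alendronate contraindications that precedes the Safety Precautions sentence. The same section also mentions a recommendation against use at GFR below 35 mL/min, but says that use in CKD-5D is not specifically named as a contraindication, so that recommendation is not counted. The list has 4 items.

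**Step 2. Match each item to a criterion.**

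| Contraindication (Potential Risks) | Matching criterion (Study Population) | Covered? |
|---|---|---|
| Oesophageal disorder that slows emptying | Exclusion in almost the same words | Yes |
| Cannot remain upright for 30 minutes | Exclusion in almost the same words | Yes |
| Hypocalcaemia | Inclusion: corrected serum calcium must be normal | Yes |
| Prior hypersensitivity to alendronate | None | No |

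Coverage is 3 of 4; 4 − 3 = 1 item is absent. The criteria run as one continuous list with no sign of redaction, so the absence does not come from removed text.

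**Step 3. Test the nearest criteria.**

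- *Bisphosphonate use in the past 6 months.* This is a washout rule about recent treatment. A patient who took alendronate earlier than that, reacted and stopped would pass it.
- *Clinical condition that may limit participation.* The examples are current illnesses. The line does not mention drug reactions and does not oblige anyone to ask about them.

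**Step 4. Who can be offered alendronate.**

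- Treatment group: 1 year, plus 1 further year in the extension, so up to 1 + 1 = 2 years.
- Control group: 1 year without study treatment, then an offer of 2 years of therapy.

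That is 2 of the 2 groups in the normal/high turnover arm. Former participants may be approached however long ago they finished, and Research Procedures allows a gap before the further therapy. The extension text describes a third consent but no repeat check of contraindications.

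**Step 5. Effect of the change.** Adding the missing exclusion takes coverage from 3 of 4 to 4 of 4 and makes the Safety Precautions sentence true.

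**The case against.** The best reply is that a contraindication can be covered without being named. The exclusion for limiting clinical conditions is open-ended, since its illnesses are only examples, and an investigator could use it to turn away a patient known to react to the arm's only study drug. The protocol also tells staff plainly that such patients should not receive alendronate. Medical history is recorded, patients have time to consult their own nephrologist, and the principal investigator has long experience with the drug. The consent forms, study drug form and prescribing information are attachments that are not shown, and they may contain an allergy check. On this reading the defect is a missing cross-reference that deserves a minor correction.

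Much of this stands as a limit on the practical risk. A careful prescriber would probably ask, and whether the attachments prompt the question cannot be judged here. It is also fair that the extension matters mainly for controls: treated patients who enter it have already had alendronate in their first year.

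It does not rescue the sentence. The sentence makes its claim about the inclusion and exclusion criteria, and those are fully visible. A general clause that could be stretched to fit does not require the check. The protocol gives two of the other contraindications their own exclusion and meets a third by an inclusion criterion. It also writes exclusions specific to teriparatide (prior skeletal radiation, radius T-score), so drug-specific screening is its own practice. No reason is given for leaving this item out, which points to an oversight.

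**Conclusion.** The concern holds. Of the four alendronate contraindications the protocol lists, the eligibility criteria cover three; prior hypersensitivity is not covered, contrary to the statement in Safety Precautions.

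The conclusion assumes only that the sentence refers to the list in Potential Risks, the sole candidate. The number of patients affected cannot be computed, because the documents give no frequency of prior hypersensitivity; it is likely to be small. No meaningful bias in the primary comparison is claimed. The IND, the monitoring, the stopping rules and DSMB oversight limit harm once treatment has begun, but they do not screen. The correction should be made because the statement is a safety assurance and the remedy is trivial.

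**What to change.** Add to the exclusion criteria, for the normal/high turnover arm: known hypersensitivity to alendronate.

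- Apply it after turnover status is known and before randomisation, to every patient in that arm. Future controls are then screened on the same terms as treated patients, and nobody has to be removed from one group only after allocation.
- For controls already randomised, ask the same question at the third (extension) consent, before alendronate is started.
- With this in place the Safety Precautions sentence can stay as it is.

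The cost is one line in the criteria and one screening question, repeated once at the extension consent. Sample size, visit schedule and analysis do not change.

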Table 2. Detail of Blood Draws for Monitoring Safety and Compliance and Secondary Endpoint Serum Biochemical Parameters
Teriparatide

Treatment Group Base-line Bi-weekly visits until steady state Q1 Visit Q2 Visit Q3 Visit 1 Year 15 mo 18mo 21mo 2 yr
or Safety: Serum Calcium & PTH X X X X X X X X X X X X

For Compliance: BSAP X X X X X X X X X X

Secondary Endpoints: FGF23, P1NP, Sclerostin, DKK-1 & PTH Ratio X X X X X

Alendronate

Treatment Group Base-line Monthly visits until steady state Q1 Visit Q2 Visit Q3 Visit 1 Year 15 mo 18mo 21mo 2yr

For Safety and Compliance: BSAP X X X X X X X X X X

Secondary Endpoints: Serum Calcium, PTH & PTH Ratio, FGF23, P1NP, Sclerostin, DKK-1 X X X X X

Standard of Care Controls Base-line Q2 Visit 1 Year 15mo 18mo 21mo 2 yr

Secondary Endpoints: All of the above Serum Biochemical Parameters X X X X X

Cinacalcet will be adjusted in 30 mg steps up to a maximum daily dose of 180 mg if needed to keep intact PTH at levels less than 200 pg/mL. If by six weeks, this fails to achieve PTH levels less than 200 pg/mL, patients will be excluded from further study participation. In the rare case where PTH level maintenance requires cinacalcet doses that induce serum calcium levels below 8.5 mg/dL, treatment will cease for two weeks after which calcium will be re-measured. At two weeks if calcium remains below 8.5 mg/dL, patients will be excluded from further participation in the study. If calcium is normalized, cinacalcet will be reinstated at half of the prior dose. Calcium will be checked again at the next monitoring visit. If at any measurement point PTH levels are less than 60 pg/mL cinacalcet will be withheld and reinstated if levels are again above 200 pg/mL.

Treatment Protocol for Alendronate: Patients with normal or high bone turnover will receive a starting dose of 35 mg alendronate p.o. once per week. Patients will be carefully instructed to follow the manufacturer's recommendations for administration. Serum calcium will be rechecked 1 week +/- 3 days after starting therapy. Dosage will be adjusted according to changes in the bone turnover marker

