Adverse events (AE's). Adverse events are any untoward medical occurrences associated with the use of study drugs, whether or not considered drug related; this includes adverse reactions (AR's) which are undesirable effects reasonably associated with use of a study drug. The severity of all anticipated (see potential risks listed above) and unanticipated AE's and AR's will be graded according to the National Cancer Institute's Common Toxicity Criteria, version 2.0 (CTC-2) (<http://ctep.cancer.gov/reporting/ctc.html>). Study coordinators (certified physician assistants) will record all adverse events at each encounter with the patient and assign a preliminary severity and attribution grade. The PI will review all adverse events and confirm their grading.

The grades of AE and AR severity will be:

0 = No AE/ARs or within normal limits,

1 = Mild AE/AR

2 = Moderate AE/AR

3 = Severe and undesirable AE/AR

4 = Life-threatening or disabling AE/AR

5 = Death related to AE/AR.

The attribution of the AEs and ARs to the study treatments will be graded as:

1 = Unrelated, AE/AR clearly not related to the investigation

2 = Unlikely, AE/AR doubtfully related to the investigation

3 = Possible, AE/AR may be related to the investigation

4 = Probable, AE/AR likely related to the investigation

5 = Definite, AE/AR clearly related to the investigation.

All AEs and ARs will be recorded in the REDCap® database. The investigator and the study coordinators will review the occurrence of mild to moderate AEs and ARs every 3 months. This file will be accessible upon request to the Data and Safety Monitoring Board. All severe or higher (grade 3-5) AEs and ARs (SAEs and SARs) will be reported to the IRB, the Data and Safety Monitoring Board, and the NIH within 48 hours, according to UK policies, and to the FDA in accordance with IND regulations. All unanticipated AEs and ARs, regardless of attribution, will be reported to the IRB, CCTS, DSMB and the NIH in an expedited manner (48 hours) if they are grade 2 or higher in severity.

[Back to Top](#)

Subject Complaints: Describe procedures (other than information provided in consent document) for handling subject complaints or requests for information about the research. The procedures should offer a safe, confidential, and reliable channel for current, prospective, or past research subjects (or their designated representative) permitting them to discuss problems, concerns and questions, or obtain information.

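### The adverse-event definition is tied to study-drug use and so, read literally, leaves out untreated controls; the controls' adverse-event contact schedule is also unsettled

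*Combined protocol and SAP*

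**What the plan says.** Under Data and Safety Monitoring, Safety monitoring: "Adverse events are any untoward medical occurrences associated with the use of study drugs", with the qualifier "whether or not considered drug related". Study coordinators "will record all adverse events at each encounter with the patient". Attribution is graded against the study treatments. Events of grade 3 to 5 go to the IRB, the safety board and the NIH within 48 hours.

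Under Research Procedures, Treatment Protocols, low-turnover patients are "randomized to receive daily teriparatide injections with cinacalcet or no study treatment, i.e. standard of care, as controls", and normal- or high-turnover patients are "randomized to receive alendronate or no study treatment, i.e., standard of care, as controls". No placebo is mentioned.

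Table 2, which lists blood draws, has these column headings:
- Teriparatide: "Base-line Bi-weekly visits until steady state Q1 Visit Q2 Visit Q3 Visit 1 Year"
- Alendronate: "Base-line Monthly visits until steady state Q1 Visit Q2 Visit Q3 Visit 1 Year"
- Controls: "Standard of Care Controls Base-line Q2 Visit 1 Year 15mo 18mo 21mo 2 yr"

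Only the two treated groups have a row for safety.

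Two other places describe contact for adverse events. Study Design plans telephone calls at least monthly and names no group. Safety Precautions plans monthly telephone or personal contact, then a health assessment every three months with blood drawn for safety, again without naming a group.

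**The concern.** The qualifier removes the need for causation but keeps the link to drug use. A control patient uses no study drug, and the text gives no separate definition for controls. Anyone applying the rule as written could leave a control's fracture or hospital admission out of the adverse-event file. Because attribution and expedited reporting use the same terms, it is also unclear whether severe control events must go to the safety board.

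Recording at encounters adds a second problem if one group has more encounters than the other, since mild, short-lived or laboratory-only events are found more often where patients are seen more often.

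Dialysis patients have heavy background morbidity, and the drugs are given under an IND. The untreated control year is the only randomised source of background rates. If control events are missed, background illness in treated patients can look like drug harm.

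**Working it through.** The plan states no figure of its own to reproduce. The check sets the texts side by side and counts contacts in year 1, because controls are offered treatment after that.

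**1. Definition against allocation.** The event must be associated with use of a study drug; controls have no study drug. On a literal reading control events fall outside, whatever their cause.

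**2. Scheduled study visits and checks after baseline, year 1** (Table 2 and the treatment protocols).
- Alendronate: 1-week calcium check (1) + months 1 and 2 (2) + Q1, Q2, Q3 and 1 year (4), with month 3 coinciding with Q1 = 7.
- Teriparatide: 1-week check (1) + bi-weekly visits until steady state (*b*) + 4 quarterly = 5 + *b*. The documents give no *b*. Assuming *b* = 2 to 6 gives 7 to 11.
- Controls: 6 months and 1 year = 2.
- Ratios to control: 7/2 = 3.5 up to 11/2 = 5.5.

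**3. Adding a monthly adverse-event contact for everyone,** with quarterly visits coinciding with months 3, 6, 9 and 12.
- Controls: 12.
- Alendronate: 12 + the 1-week check = 13; 13/12 = 1.1.
- Teriparatide: 12 + 1 + *b* = 15 to 19; 15/12 = 1.25 and 19/12 = 1.6.

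**4. How much it matters who gets the monthly contact.** This is an illustration; its assumptions do not come from the documents. Let non-serious events occur uniformly over 52 weeks and be reported at the next contact, with recall decaying at half-life *h*. With intervals *L* between contacts and *k* = ln 2 / *h*, the share captured is (1/52) × Σ(1 − e^(−*kL*))/*k*. Taking *b* = 3 and *h* = 1, 3 and 6 months:

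| Schedule | 1 month | 3 months | 6 months |
|---|---|---|---|
| Teriparatide, with monthly contact | 0.746 | 0.903 | 0.950 |
| Alendronate, with monthly contact | 0.729 | 0.896 | 0.946 |
| Control, with monthly contact | 0.721 | 0.893 | 0.944 |
| Control, two visits only | 0.237 | 0.541 | 0.721 |

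Control capture relative to teriparatide is 0.97 to 0.99 if controls get the monthly contact, and 0.32, 0.60 and 0.76 if they do not. Against alendronate, with monthly contact in both groups, it is 0.99 to 1.00.

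**5. Do controls get it?** Safety Precautions names no group, which suggests yes. But the quarterly safety draws in the same paragraph do not fit Table 2, where controls have no Q1 or Q3 column. Study Design lists the calls beside the treatment monitoring visits. The rules for acting on complaints raised at these contacts appear only under the teriparatide and alendronate headings. The text leaves the answer open.

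**6. Laboratory events.** A telephone call cannot detect them. Teriparatide patients have calcium checked at one week, bi-weekly and then quarterly; controls have year-1 draws at 6 and 12 months only. Equal calls would not remove this difference.

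**The case against.** A reader might infer from the definition that controls can have no adverse events and will be counted as zero. The documents do not go that far. The qualifier drops causation, one attribution grade is for events clearly unrelated to the investigation, and the instruction to coordinators is not limited to treated patients. Nothing tells staff to ignore control events. The gap is in the wording, and practice may differ.

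A reader might also take the 3.5- to 5.5-fold visit ratio as the gap in recording opportunities. That is not supported either. Table 2 schedules blood draws, and a draw may be taken by dialysis staff without an adverse-event interview. The main channel is the monthly contact, which on its face includes controls and brings the ratio down to 1.1 to 1.6.

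Nor do the documents show that safety cannot be compared. Deaths and other severe events depend little on visit frequency, and the available text specifies no between-group safety analysis for this to invalidate. Any leftover bias would overstate harm in treated patients, which is the cautious direction for a safety signal.

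These points limit the size of the problem. They do not bring controls within the definition, they do not resolve the conflict between Safety Precautions and Table 2, and they do not address laboratory-detected events.

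**Conclusion.** The point holds as a defect in wording and scheduling that puts control ascertainment at risk. The definition does not cover the comparator group as written, and the sections disagree on which contacts controls receive. Control events may be under-counted, chiefly mild to moderate and laboratory-detected ones.

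The size depends on one unsettled fact. If the monthly contact reaches controls, the imbalance in contacts is small. If it does not, the loss of non-serious control events could be substantial under the recall model above. The teriparatide figures rest on the assumed 2 to 6 bi-weekly visits, and the capture figures on the assumed recall half-lives. The consequence applies to any between-group comparison that is made, since none is specified.

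**What to change.** 1. Define an adverse event as any untoward medical occurrence in any randomised participant, from randomisation, with or without study drug. Apply the same severity grading and reporting rules to controls.
2. State that the monthly contact, with the same questions, applies to all groups. Reconcile the contact and visit schedules in Study Design, Safety Precautions and Table 2 so that the control schedule appears once and consistently.
3. Base between-group event rates on those common contacts. List separately the events found only at extra treatment visits or extra laboratory draws.

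The cost is revised wording and slightly more recording in controls. On the natural reading of Study Design and Safety Precautions, the monthly contacts are already planned.
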